5.3 Exclusion Criteria

1. Target Disease Exclusion
 - a) Subject has a history of basilar migraine, hemiplegic migraine, retinal migraine or migraine accompanied by diplopia or decreased level of consciousness as defined by International Classification of Headache Disorders, 3rd Edition⁷.
 - b) Subjects with headaches occurring 15 or more days per month (migraine or non-migraine) in any of the 3 months prior to the Screening Visit.
2. Medical History and Concurrent Diseases
 - a) Subject history with current evidence of uncontrolled, unstable, or recently diagnosed cardiovascular disease, such as ischemic heart disease, coronary artery vasospasm, and cerebral ischemia. Subjects with myocardial infarction (MI), acute coronary syndrome (ACS), percutaneous coronary intervention (PCI), cardiac surgery, stroke, or transient ischemic attack (TIA) during the 6 months (24 weeks) prior to the Screening Visit.
 - b) Uncontrolled hypertension (high blood pressure) or uncontrolled diabetes. However, subjects can be included who have stable hypertension and/or diabetes for 3 months (12 weeks) prior to the Screening Visit. Blood pressure greater than 150 mm Hg systolic or 100 mm Hg diastolic after 10 minutes of rest at the screening or baseline visit is exclusionary. Blood pressure measurement may be repeated once at screening visit and baseline to confirm reproducibility.
 - c) Subjects with major depressive (MDD) or any anxiety disorder (AD) which require more than 1 daily medication for each disorder or subjects with major depressive episode

(MDE) within last 12 months. Medications to treat major depressive disorder or an anxiety disorder must have been at a stable dose for at least 3 months prior to the Screening Visit.

- d) Active chronic pain syndromes (such as fibromyalgia, chronic pelvic pain, complex regional pain syndrome [CRPS]).
- e) Subjects with other pain syndromes (including trigeminal neuralgia), psychiatric conditions, dementia, or significant neurological disorders (other than migraine) that, in the Investigator's opinion, might interfere with study assessments of safety or efficacy.
- f) Subject has a history of gastric, or small intestinal surgery (including Gastric Bypass, Gastric Banding, Gastric Sleeve, Gastric Balloon, etc.), or has a disease or condition (e.g., chronic pancreatitis, ulcerative colitis, etc.) that causes malabsorption.
- g) Subject has a history or diagnosis of an active hepatic or biliary disorder.
- h) The subject has a history or current evidence of any unstable medical conditions (e.g., history of congenital heart disease or arrhythmia, known or suspected infection, hepatitis B or C, or cancer) that, in the investigator's opinion, would expose them to undue risk of a significant adverse event (AE) or interfere with assessments of safety or efficacy during the course of the study.
- i) History of, treatment for, or evidence of, alcohol or drug abuse within the past 12 months (48 weeks) or subjects who have met DSM-V criteria⁸ for any significant substance use disorder within the past 12 months (48 weeks) from the date of the Screening Visit according to PI assessment.
- j) History of use of narcotics such as opioids (morphine, codeine, oxycodone, hydrocodone) or barbiturate- (e.g., butalbital) containing medication for ≥ 4 days per month during the 3 months (12 weeks) prior to the Screening Visit.
- k) Subjects should be excluded if the subject has reported current use of, or has tested positive at the Screening visit for, drugs of abuse (amphetamines, barbiturates, benzodiazepines, cannabinoids, cocaine, methadone, opiates, MDMA, methamphetamines, oxycodone, phencyclidine). In addition:
 - i. Detectable levels of cocaine and phencyclidine (PCP) in the drug screen are exclusionary. Retesting is not allowed.
 - ii. Subjects who are positive for amphetamines, and who are on a prescribed amphetamine medication for an approved indication (e.g., ADHD) will be allowed into the study at the Investigator's discretion. This determination by the Investigator must be well documented in the subject's source medical records. The stimulant dose must be stable from 3 months (12 weeks) prior to the Baseline Visit until the Week 24 or EOT Visit occurs.

iii. Detectable levels of marijuana in the drug screen are not exclusionary, if in the investigator's documented opinion the subject does not meet DSM-V criteria⁸ for substance use disorder, and the positive test does not signal a clinical condition that would impact the safety of the subject or interpretation of the study results. Subject must agree to refrain from marijuana use during the study.

l) Hematologic or solid malignancy diagnosis within 5 years prior to the Screening Visit. Subjects with a history of localized basal cell or squamous cell skin cancer are eligible for the study if they are cancer-free prior to the Screening Visit in this study.

m) Subject has current diagnosis of major depressive disorder requiring treatment with atypical antipsychotics, schizophrenia, bipolar disorder, or borderline personality disorder.

n) Body mass index $> 35.0 \text{ kg/m}^2$.

3. History of anaphylaxis to any substance or a clinically important reaction to any drug.

4. Sex and Reproductive Status

a) WOCBP who are unwilling or unable to use an acceptable contraceptive method or abstinence to avoid pregnancy for the entire study and 28 days after last dose of study drug.

b) Women who are pregnant or breastfeeding.

c) Women with a positive pregnancy test at screening or prior to study drug administration.

5. ECG and Laboratory Test Findings

a) Estimated glomerular filtration rate (eGFR) according to the re-expressed abbreviated (four-variable) Modification of Diet in Renal Disease (MDRD) Study equation $< 30 \text{ mL/min/1.73m}^2$.

b) Abnormal ECG that in the investigator's opinion makes the subject unsuitable for a clinical trial (e.g. Corrected QT interval $> 470 \text{ msec}$).

c) Total bilirubin $> 1.5 \times \text{ULN}$ (For Gilbert's syndrome, direct bilirubin $> \text{ULN}$ is exclusionary).

d) AST or ALT $> 1.5 \times \text{ULN}$.

e) Serum albumin $< 2.8 \text{ g/dL}$.

f) Neutrophil count $\leq 1000/\mu\text{L}$ (or equivalent).

g) HbA1c $> 7.5\%$.

6. Prohibited Medications

- a) History of use of analgesics (e.g., nonsteroidal anti-inflammatory drugs [NSAIDs] or acetaminophen) on \geq 15 days per month during the 3 months (12 weeks) prior to the Screening Visit.
- b) Use of medication accepted for treatment of acute migraine ([Section 5.5.2](#)) for a non-migraine indication on \geq 15 days per month during the 3 months (12 weeks) prior to the Screening Visit.
- c) Subjects taking a prohibited medication (Refer to [Section 5.4](#)).

7. Other Exclusion Criteria

- a) Prisoners or subjects who are involuntarily incarcerated.
- b) Subjects who are compulsorily detained for treatment of either a psychiatric or physical (e.g., infectious disease) illness.
- c) Exposure to non-biological investigational agents (other than rimegepant) within the 30 days prior to the Screening Visit.
- d) Exposure to biological investigational agents within 3 months (12 weeks) prior to the Screening Visit.
- e) Subjects who meet criteria for C-SSRS Suicidal Ideation Items 4 or 5 within the last 12 months prior to screening, OR subjects who endorse any of the 5 C-SSRS Suicidal Behavior Items (actual attempt, interrupted attempt, aborted attempt, preparatory acts, or behavior) within the last 10 years prior to the Screening Visit, OR subjects who, in the opinion of the investigator, present a serious risk of suicide (See [Section 6.2.5](#)).
- f) Previous enrollment in any multiple dose BHV3000 (rimegepant) study, such as BHV3000-201, BHV3000-305, or BHV3000-404 regardless of the number of doses taken. Subjects may be considered for BHV3000-405 (C4951011) if the subject participated in any of the following single dose studies: BHV3000-301, BHV3000-302, BHV3000-303. Note that subjects who were considered screen failures in a past BHV3000 study may be considered after discussion with the Sponsor and written approval is received.
- g) Subjects are excluded if they have had no therapeutic response with $>$ 2 of the 8 medication categories for prophylactic treatment of migraine listed in [Appendix 3](#) after an adequate therapeutic trial. Additional details can be found in [Section 16.3 Appendix 3](#).
- h) Participation in any other investigational clinical study while participating in this clinical study. Participation in a COVID-19 mRNA vaccine study (vaccine must be authorized

under FDA emergency use authorization or approval) who are at least 30 days post last dose of the vaccine are permitted to be screened for this study.

- i) Past participation in a clinical study within 30 days prior to the Screening Visit. Note: Individuals who do not meet the criteria for participation in this study (screen failure) may be considered for re-screening in select circumstances (e.g., previously pregnant, screening window too long, ineligibility was due to 1 of the eligibility criteria that may have changed due to medical intervention or 1 of the eligibility criteria modified in a protocol amendment). In all possible re-screening circumstances, the situation must be discussed with the Sponsor prior to re-screening, with approval in writing from the Sponsor prior to re-screening.
- j) Please see [Section 5.4](#) for prohibited medications and [Section 5.5.2](#) for permitted acute migraine medications.
- k) Investigator site staff directly involved in the conduct of the study and their family members, site staff otherwise supervised by the investigator, and sponsor and sponsor delegate employees directly involved in the conduct of the study and their family members.

5.4 Prohibited and Restricted Concomitant Medications and Devices

All medications taken by subjects after screening until the last study day will be documented as concomitant medications including vaccinations.

The medications and devices listed below are prohibited starting at the Baseline Visit and during the course of this study or as specified.

1. St. John's Wort should not be taken 14 days prior to the Baseline Visit and throughout the study.
2. Butterbur root or extracts should not be taken 14 days prior to the Baseline Visit and throughout the study.
3. History of use of ergotamine medications on \geq 10 days per month on a regular basis for \geq 3 months (\geq 12 weeks). Note that use of ergotamine medication is prohibited throughout the entire duration of the study (Screening Visit to Follow-up Week 8 Visit), however reporting of any use of ergotamine medication is required for the purpose of defining migraine days.
4. Use of narcotic medication, such as opioids (e.g., morphine, codeine, oxycodone, and hydrocodone) or barbiturates is prohibited starting from 2 days prior to the Baseline Visit and throughout the study, including the Follow-up Week 8 Visit.
5. Use of acetaminophen or acetaminophen containing products for non-headache indications after the Baseline Visit is prohibited. Any use of acetaminophen or acetaminophen containing products for non-headache indications during the Screening Phase must be stopped at least 2 days prior to Baseline Visit. Acetaminophen as acute headache medication as described in [Section 5.5.2](#) is allowed during the study.
6. The use of CGRP antagonists (biologic [e.g., Aimovig[®] or Ajovy[®]] or small molecule [e.g., Nurtec[®] ODT or UbrelvyTM]) other than rimegepant provided for this clinical study is prohibited during the study including through the Follow-up Week 8 Visit.
7. Use of marijuana and all forms of ingested or inhaled cannabidiol (CBD) and THC-containing products are prohibited during the study.
8. Concomitant use of moderate to strong CYP3A4 inhibitors is prohibited during the study. If use of a moderate or strong CYP3A4 inhibitor is required, such as use of HIV Protease Inhibitors, Hepatitis C protease inhibitors, certain azole antifungals, or clarithromycin, dosing with rimegepant should be stopped and should not start again until 14 days after the last dose of the moderate or strong CYP3A4 inhibitor. Please see [Section 16.2 Appendix 2](#).

9. Concomitant use of moderate to strong CYP3A4 inducers is prohibited during the study. If use of a moderate or strong CYP3A4 inducer is required, such as use of carbamazepine, phenytoin, or rifampin, dosing should be stopped and should not start again until 14 days after the last dose of the moderate or strong CYP3A4 inducer. Please see [Section 16.2 Appendix 2](#).
10. Concomitant use of atypical antipsychotics such as Abilify (aripiprazole), Zyprexa (olanzapine), Seroquel (quetiapine), Geodon (ziprasidone), or Risperdal (risperidone) or Depakote/Depakene (valproic acid/valproate) is prohibited during the study.
11. Concomitant use of LAMICTAL (lamotrigine) is prohibited during the study.
12. Use of analgesics other than acetaminophen for non-migraine use (e.g., nonsteroidal anti-inflammatory drugs [NSAIDs]) on ≥ 15 days per month is prohibited during the study. Use of acetaminophen or acetaminophen containing products for non-headache indications after the Baseline Visit is prohibited.
13. Use of CefalyTM or any other device for migraine treatment within 12 weeks of the Screening Visit.
14. Use of any investigational agent other than rimegepant (provided for the purpose of this clinical study) from the Screening Visit through the Follow-up Week 8 Visit.
15. Concomitant use of strong inhibitors of the P-gp transporter with rimegepant is prohibited during the study.

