4.3.1 Screening Phase

The Screening Phase will be 3-14 days and will have 1 scheduled visit, the Screening Visit, which should be completed in person. Subjects will undergo all screening procedures as detailed in [Table 1](#).

Before any study procedures are performed, subjects must provide documented informed consent. After informed consent, subjects will be enrolled in the IWRS system. The subject's migraine history and medical history will be collected at the Screening Visit.

All subjects will continue to use their standard of care migraine medications (both prophylactic and acute, prescribed and OTC) during the Screening Phase. Subjects will record all concomitant medications, including standard of care migraine medications (both prophylactic and acute, prescribed and OTC), in a concomitant medication paper diary.

The duration between the Screening Visit and the Baseline Visit is 3-14 days. Every effort should be made to perform the Baseline Visit after as soon as the screening laboratory results are available and within the 14 days.

Individuals who do not meet the criteria for participation in this study (screen failure) may be considered for re-screening in select circumstances (e.g., previously pregnant, screening window too long). Subjects who were considered screen failures previously may be considered for re-screening provided the ineligibility was due to one of the eligibility criteria that may have changed due to medical intervention or one of the eligibility criteria modified in a protocol amendment. Adequate documentation in source records must support the previously failed criteria. In all possible re-screening circumstances, the situation must be discussed with the Sponsor prior to re-screening, with approval in writing from the Sponsor prior to re-screening. If a subject is approved for re-screening, a new subject number must be obtained from the appropriate study-related system. Re-screening will only be permitted one time.

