 - Ergotamine taken on or after informed consent
 - Lamotrigine taken on or after informed consent
 - Narcotic (barbiturate or opioid) taken up to 2 days before study drug start or afterward #
 - Rimegepant taken on or after study drug start
 - Select moderate or strong cytochrome P450 3A4 (CYP3A4) inducer taken on or after informed consent #

- Select strong CYP3A4 inhibitor taken on or after informed consent #.

For the subcategories marked with “#”, preferred names are displayed alphabetically as additional subcategories. Medications taken up to X days before a reference date or afterward are defined as those with imputed medication start date or imputed end date \geq reference date – X . Refer to the Core SAP for additional details about prohibited non-study medications.

The protocol version to which subjects originally consented is determined from the Demographics/Informed Consent CRF.

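### The 14-day interval off moderate or strong CYP3A4 inhibitors and inducers applies to a rimegepant restart but not to the first dose, which can follow after 1–2 days

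*Protocol*

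**What the plan says.** Protocol 5.4 item 8 bars moderate to strong CYP3A4 inhibitors during the study. If one is needed, rimegepant is stopped and "should not start again until 14 days after the last dose of the moderate or strong CYP3A4 inhibitor". Item 9 says the same for inducers: "should not start again until 14 days after the last dose of the moderate or strong CYP3A4 inducer". Both sentences concern a subject already on treatment.

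For the period before treatment:

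- **Start of the ban.** The lead-in to 5.4 reads "The medications and devices listed below are prohibited starting at the Baseline Visit and during the course of this study or as specified". Items 8 and 9 name no earlier start.
- **Eligibility.** Exclusion 6c covers "Subjects taking a prohibited medication", which is current use with no look-back.
- **Timing.** Protocol 4.3.1: "The duration between the Screening Visit and the Baseline Visit is 3-14 days". It also urges sites to hold Baseline promptly once laboratory results are back. Under 4.3.2.1 the first dose may be on the Baseline day or the next day.
- **SAP 9.1** counts two CYP3A4 categories as deviations, both from consent: "Select moderate or strong cytochrome P450 3A4 (CYP3A4) inducer taken on or after informed consent" and "Select strong CYP3A4 inhibitor taken on or after informed consent".

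Pre-dose intervals do exist for particular drugs or uses: St. John's Wort and butterbur (5.4 items 1 and 2, 14 days before Baseline), barbiturates (item 4, 2 days before Baseline) and discontinued oral migraine prophylactics (inclusion 1e iii, 30 days before Screening).

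**The concern.** The protocol treats 14 days off an interacting drug as the condition for resuming rimegepant, yet sets no such condition for beginning it. The documents give no reason for the difference.

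The treatment of inducers is also uneven. Appendix 2 puts St. John's Wort, phenobarbital, rifampin, carbamazepine and phenytoin in one list of strong inducers. Before a first dose, St. John's Wort has 14 days, phenobarbital (as a barbiturate) has 2, and rifampin has none. Carbamazepine and phenytoin have none either, unless the drug was an oral migraine prophylactic.

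At stake is rimegepant exposure, and adverse events, in roughly the first two weeks for the few subjects concerned. The study is a required post-marketing safety study of daily dosing without dose adjustment.

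**Working it through.** The check is calendar arithmetic. The plan's own figure is the 14-day restart interval, which is a rule and not a calculated value. Dosing may resume on day 14 after the last interacting dose, so days 1 to 13 are barred.

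**Inputs**
- S, days from Screening to Baseline: 3 to 14 (Protocol 4.3.1).
- d, days from Baseline to first dose: 0 or 1 (Protocol 4.3.2.1).
- Planned treatment: 168 days (Week 24 is Day 168 in Protocol Table 1).

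**Reading A: ban from Baseline (literal 5.4 lead-in).** The last permitted interacting dose is the day before Baseline, so gap = 1 + d, which is 1 or 2 days whatever S is. Shortfall: 14 − 1 = 13 or 14 − 2 = 12 days. Eligibility is checked at Screening and at Baseline, but a course taken wholly between the two visits is not current use at either.

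**Reading B: ban from Screening or consent.** Support for this reading is the SAP's counting from consent and a note on ergotamine in 5.4 item 3, which describes the study as starting at Screening. The last permitted dose is the day before Screening, so gap = S + 1 + d.
- Minimum: 3 + 1 + 0 = 4 days; shortfall 14 − 4 = 10 days.
- A gap of at least 14 needs S ≥ 13 with a same-day start, or S ≥ 12 with a next-day start.
- If a dose on the Screening day before consent is tolerated, the minimum falls to 3 days.

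| | Shortest gap | Shortfall | Dosing days inside the window |
|---|---|---|---|
| A: from Baseline | 1 day | 13 days | days 1–13: 13 of 168 = 7.7% |
| B: from Screening or consent | 4 days | 10 days | days 4–13: 10 of 168 = 6.0% |

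The last column is the calendar limit for a single worst-case subject. It is not a proportion of subjects or a measure of any study effect.

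**Who is left uncovered.** Besides the intervals listed above, there is partial cover from:
- exclusion 2b: hypertension or diabetes stable for 12 weeks;
- exclusion 2c: antidepressant or anxiety medication at a stable dose for 3 months;
- exclusion 2g: active hepatic or biliary disorder;
- exclusion 2h: unstable conditions, including infection and hepatitis B or C, on investigator judgment;
- exclusion 2l: malignancy within 5 years.

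The residue is mainly short courses just completed, such as clarithromycin, erythromycin, ciprofloxacin or fluconazole, all listed in Appendix 2. The documents give no figure from which to count such subjects.

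**The case against.** The best reply is that the two situations differ. A restart follows an interruption in a treated subject. A first dose follows medical history, laboratory tests, an ECG and two eligibility checks. Where the sponsor wanted an interval before Baseline it wrote one (5.4 items 1, 2, 4 and 5), so silence in items 8 and 9 may be deliberate. This has some force, but item 1 cuts the other way: it applies 14 days before Baseline to a drug that the protocol itself lists as a strong CYP3A4 inducer.

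It can also be said that no harm is shown, which is correct. Three stronger readings are tempting, and the documents support none of them:

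- **That drug interaction persists for 14 days and distorts early safety data.** No rationale for the 14 days is given. It serves here only as the protocol's own standard. No effect on the Week 2 laboratory tests or ECG is shown.
- **That such use would go unseen.** Use during Screening goes into the concomitant medication diary, and SAP 9.1 counts inducers and strong inhibitors from consent. Use before consent may appear in the listing under SAP 6.2.6.3. Its definitions, and further detail on prohibited medications, are in the Core SAP, which is not among the documents.
- **That many subjects are exposed.** The partial safeguards narrow the group considerably.

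Finally, an amendment helps only future subjects. SAP Version 8 is dated 05-Sep-2024, more than a year after Protocol Version 6, and the documents do not give enrolment status. That limits the value of the change.

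**Conclusion.** The gap in the text is real: 14 days before a restart and no general interval before the first dose. The shortest permitted gap is 1–2 days on the literal reading and 4 days if the ban runs from Screening or consent. These figures assume a last interacting dose on the last permitted day; the 4-day figure also assumes a 3-day Screening Phase and a same-day start. The text leaves some doubt about which reading is meant, but neither secures 14 days.

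The consequence is small. It concerns early treatment days in an unknown and probably small number of subjects, and nothing shows that a study conclusion would change. It is worth correcting because a site can comply fully and still dose inside an interval that the protocol forbids at restart, and because the correction is cheap. It ranks as an optional improvement.

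**What to change.** **Protocol 5.4, items 8 and 9.** State that rimegepant must not be started or restarted until at least 14 days have passed since the moderate or strong CYP3A4 inhibitor (item 9: inducer) was last taken. Tie the interval to the first dose and say at least 14 days. Wording such as within 14 days before Baseline could be read to bar a last dose exactly 14 days earlier, which the restart rule allows.

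**SAP 9.1, optional.** For the CYP3A4 categories already listed, count use fewer than 14 days before study drug start, or afterward. The SAP's rule flags an imputed start or end date on or after the reference date minus X, so X should be 13: a last dose 14 days before is not flagged and one 13 days before is. Apply this only to subjects who originally consented to the amended version, as SAP 9.1 already does for eGFR and BMI.

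**Cost.** One phrase in each item, plus a look-back date and a consent-version condition if the SAP is changed. With a same-day start, a last dose k days before Screening needs S ≥ 14 − k:
- k = 1 needs S = 13, which is 10 days later than the 3-day minimum;
- k = 0 needs S = 14, which is 11 days later.

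Both fit the permitted Screening Phase. A last dose j ≥ 1 days after Screening needs S ≥ 14 + j with a same-day start, which exceeds 14. A next-day start gains one day, so j = 1 just fits (14 − 1 + 1 = 14). Beyond that the subject would need the single permitted re-screen, with written Sponsor approval. Only subjects enrolled after the amendment benefit.
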